*Clinic visit is to teach and monitor form for strength exercises, to assess for safety concerns during treatment, and to coordinate with health promotion clinic staff counselor (see Figure 3 in Significance)

†Phone counseling delivered by health promotion clinic staff

12.3h. PRELIMINARY DATA PERTINENT TO THE APPLICATION

I and other study team members have collected study data in primary care clinical settings and clinical trial settings that demonstrate the feasibility of collecting the proposed measures. In addition, these data suggest that the proposed screening and behavioral intervention can be implemented in primary care systems that use health promotion clinic staff. Finally, these data suggest that the proposed intervention will improve the proposed physical activity measures that are strongly linked to physical function.

Preliminary data – Behavioral counseling by health promotion clinic staff I led an RCT for patients with uncontrolled hypertension of an intervention that included health promotion clinic staff counseling. Health promotion clinic staff called intervention patients and delivered brief, tailored counseling about lifestyle measures to control blood pressure, and arranged a primary care clinic visit.⁵⁴ We did not contact usual care patients. Because this intervention improved process outcomes related to blood pressure control and had high acceptability to patients and clinicians,⁵⁴ our clinics have continued this hypertension management process.

Table 9 Population Characteristics for Preliminary Data on Correlations between Physical Function and Physical Activity	
	Overweight, sedentary adults (n = 12)
T2D (%)	58
Age (years, mean (SD))	61.1 (5.4)
BMI (kg/m ² , mean (SD))	30.2 (2.6)
Accelerometer-measured Physical activity (Combined moderate-vigorous intensity minutes/week, mean (SD))	91.0 (97.3)
Cardiorespiratory fitness (maximal oxygen uptake, ml/kg/min)	21.9 (1.5)
Physical function: Rapid, timed 400-meter walk, seconds (mean, SD)	300.4 (56.7)

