Preliminary data -Physical activity and physical function outcome measures I have preliminary unpublished data on physical activity, physical fitness and physical function performance data in an ongoing study of sedentary, overweight older adults aged 50-70 years with and without T2D (Table 9). We measured physical activity and function by methods proposed in this application — accelerometer and the time needed to complete a 400-meter walk at the most rapid pace possible. As others have published,^{20,24,26,56-58,76} we also found strong correlations between higher levels of physical activity measured by accelerometer (K23 1° outcome) and better physical function, as measured by a shorter time required to complete a rapid 400-meter walk ($r = -0.52$). These data

support the conceptual framework of this study (Figure 2) by demonstrating the relationship between the outcomes of physical activity and function.

Preliminary data on 4-week phone-based activity counseling tailored to Dishman barriers surveys responses Separate from our preliminary data in Tables 8-9, we have pilot-tested the delivery of tailored telephone-based counseling to 3 older adults with T2D (aged 67.3 ± 7.5 years, mean \pm SD). Over 4 telephone-based counseling visits tailored to each participant's physical activity barriers responses,⁷⁷ we demonstrated an increase in combined moderate-vigorous physical activity levels by 142 minutes/week across 3 participants (from 65 ± 80 to 207 ± 87 minutes/week, mean \pm SD).

Preliminary data on improved activity and function in response to interventions

Study team mentors ([name]. [name]) have been active investigators in several, large behavioral physical activity interventions in clinical trials, primary care, and community settings that demonstrated improvements in outcomes of physical activity and physical function.⁵⁵⁻⁵⁹ These trials have all used common behavioral tools of regular, repeated staff contact with participants to set goals, track activity, and overcome barriers to activity. Some of these trials included older participants with some physical functional impairments similar to those found in the participants we propose to enroll, although our trial will be substantively different by its use of clinical staff: 1) to identify patients who might safely participate; 2) to deliver such interventions.

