Summary: Taken together the preliminary data collected support the idea that an intervention in a clinical setting which allows for screening to identify appropriate patients and then implementing a clinic based intervention has the potential to improve physical activity and function in sedentary adults with T2D.

12.3i. OUTCOME MEASURES (see Table 10 on next page)

12.3j. POWER CALCULATION AND DATA ANALYSES FOR AIM 1 (EFFECTIVENESS)

Power Calculation: We used PASS version 11 to calculate power for the physical activity outcome.⁷⁸ Aim 1 was powered based on a previously observed effect size of Cohen's $d = .61$ when comparing a physical activity intervention to an education control group on physical activity of moderate-to-vigorous intensity⁷⁹ among older, obese adults. Assuming similar sized effects in the current study and a two-sided alpha of 0.05, the proposed sample size of $n=90$ will provide over 80% power to detect differences between the activity intervention and usual care for Hypothesis 1. If our effects match that of our preliminary data (increase in combined moderate-vigorous physical activity levels by 142 minutes/week across 3 participants (from 65 ± 80 to 207 ± 87 minutes/week, mean \pm SD), then we will have over 95% power to detect differences between the activity intervention and usual care. Enrollment of $n=130$ was planned to allow for up to 30% attrition. For Aim 1b, the proposed sample size will be sufficient to obtain stable means and standard deviations in order to calculate an accurate effect size estimate for physical function outcomes.

Data analysis: Before conducting the analyses by aim, we will assess descriptively and graphically the mean and distribution of each study outcome and covariate, in order to assess for outliers and skewed distributions. If variables are not normally distributed, we will consider logarithmic transformation.

Aim 1 Data Analysis

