Hypothesis 1. Using intent to treat principles, we will test for differences between the intervention and usual care groups on physical activity at the 3 month assessment. We will assess the intervention effect size of change in physical activity from baseline testing to 3 months using an ANCOVA model with adjustment for age; covariates from Table 10 (e.g., cognitive processing speed); and each participant's baseline score. Adjustment for baseline score is useful in this relatively small RCT to eliminate any potential baseline differences between groups that may occur despite the randomization procedure. We expect that the mean physical activity at 3 months will be significantly higher in the intervention group than in the usual care control group. Every attempt will be made to ensure high retention rates at posttest, although some attrition is to be expected. The level and patterns of missing data will be evaluated relative to intervention condition and other baseline characteristics to determine whether there is systematic bias in the missing data. If necessary and appropriate, based on the level and patterns of missing data, state-of-the-art techniques (e.g., multiple imputation) will be used.

Aim 1 secondary outcomes. The analyses for Aim 1 secondary outcomes will be used to detect trends and to provide necessary data to calculate the sample size needed to detect differences in a larger RCT. We will assess the intervention effect size by calculating a Cohen's d effect size comparing the means of the two groups at the three-month follow-up. We will use separate ANCOVA models to assess pre-post intervention changes in the following outcomes listed in Table 10: physical function by 400-meter rapid gait speed (differentiates adults with higher baseline function); Short Physical Performance Battery (differentiates adults with lower baseline function); intermediate physical activity behavioral constructs from SCT; intermediate functional outcome (lower extremity strength); and metabolic outcome (Hemoglobin A1c).

Table 10. Outcome, Predictor, and Covariate Measures for [name] K23

Outcome	Instrument	Variable	Measure
Physical Activity outcomes			

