Objective physical activity	Actigraph GT3x+ accelerometer measures physical activity objectively as minutes/week of moderate intensity and vigorous intensity physical activity, respectively. ⁸⁰ We define moderate intensity levels by the methods of Freedson et al. ⁸¹ Participants will wear the Actigraph for a 7-day period pre/post intervention. We will ensure measurement during a typical 7-day period and will use standard wear-time validation procedures to ensure valid weekday and weekend data. Actigraph data will be collected on the 7 days between physical function and VO ₂ max testing.	Continuous	Aim 1 1° outcome
Physical activity behavioral constructs from SCT	Standard survey measures to assess the following physical activity behavior assessments of constructs from SCT: Self-efficacy to do physical activity of increasing duration; ^{82,83} Social-environmental support is a valid measure of how others support one's healthy lifestyle choices; ⁸⁴ Lower barrier scores on the Dishman physical activity barriers survey are associated with higher levels of physical activity; ⁷⁷ Physical Activity outcome expectancy for elders survey includes positive elements of physical activity for older adults, including health-related factors – better scores are associated with higher physical activity levels ⁸⁵	Continuous	Aim 1 Predictor variable: physical activity (PA predictor)
Physical Function outcomes			
Cardiorespiratory fitness (VO ₂ max)	To assess cardiorespiratory fitness, we measure breath-by-breath utilization of oxygen (VO ₂) and carbon dioxide (VCO ₂) with a Medgraphics Ultima CPX metabolic cart (Minneapolis, MN). We also measure blood pressure (auscultation), and cardiac status (12-lead ECG). To determine VO ₂ max, subjects perform treadmill exercise to exhaustion using a standard protocol. ^{86,87} We define VO ₂ max per standard practice. ⁸⁶	Continuous	Aim 1 2° outcome
Physical function	400-meter rapid gait speed test measures fitness and mobility; it is sensitive to change for adults with minimal to mild functional impairment ; predicts disability and mortality. ⁸⁸ Physical function measures will be assessed on a separate study date from the VO ₂ max testing.	Continuous	Aim 1 2° outcome

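### Does leaving a log transformation of the primary activity outcome open to consideration undermine the test of Hypothesis 1?

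*Combined protocol and SAP*

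**What the plan says.** The data analysis paragraph of section 12.3j has the distribution of every outcome and covariate examined before the analyses by aim. It then adds: "If variables are not normally distributed, we will consider logarithmic transformation". There is no normality criterion, no commitment to transform, no added constant, no sensitivity analysis on the other scale, and no statement on blinding of the look. Zero-minute weeks are not mentioned anywhere.

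Other parts of the plan bear on the scale:

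- The Hypothesis 1 analysis in 12.3j is an ANCOVA adjusted for the baseline score, age and Table 10 covariates. Its expected result is worded as a mean: "We expect that the mean physical activity at 3 months will be significantly higher in the intervention group".
- Table 10 says the accelerometer "measures physical activity objectively as minutes/week of moderate intensity and vigorous intensity physical activity, respectively".
- Table 9 in 12.3h reports one variable, "Combined moderate-vigorous intensity minutes/week, mean (SD"), as 91.0 (97.3) in 12 people.
- The second power scenario in 12.3j uses the three-person pilot: "increase in combined moderate-vigorous physical activity levels by 142 minutes/week across 3 participants", from 65 ± 80 to 207 ± 87.

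**The concern.** A primary analysis should have one scale, chosen without sight of the treatment comparison. Here the plan names a second scale and gives no rule for moving to it. The condition for considering the move is likely to be met, because both preliminary baseline samples have an SD larger than the mean for a quantity that cannot be negative.

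The two scales also estimate different things. ANCOVA on minutes compares mean minutes; ANCOVA on logs compares geometric means. A log cannot take a zero, so anyone with no moderate-to-vigorous minutes needs an added constant, and its size affects the answer. Two careful analysts who both keep every randomised participant could therefore differ on whether Hypothesis 1 reaches p < 0.05.

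Table 10 adds a smaller doubt. By listing moderate and vigorous minutes respectively, it could be read as giving two primary variables rather than one.

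**Working it through.** **Inputs from the plan.** d = 0.61, two-sided alpha 0.05, 90 analysed (45 per arm with 1:1 allocation), all from 12.3j and 12.3e. Mean 91.0 and SD 97.3 come from Table 9; 65 ± 80 comes from the pilot.

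**Inputs assumed.** Pre-post correlation 0.5; gamma or lognormal shape; 0% to 20% zero-minute weeks; additive, proportional or half-responder effect. The plan gives none of these.

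**1. The plan's power.** A two-sample t test with noncentrality 0.61 × √(45/2) = 2.89 and 88 df has power 81.6%. The stated figure of over 80% is reproduced.

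**2. Is skew likely?** Normal curves with the plan's moments put Φ(−91/97.3) = 17.5% and Φ(−65/80) = 20.8% of people below zero minutes. A non-negative variable has skewness of at least CV − 1/CV. That is 1.069 − 0.935 = 0.13 for Table 9 and 1.231 − 0.8125 = 0.42 for the pilot. Some right skew is therefore forced if those moments hold. The figure after counseling, 207 ± 87 (CV 0.42), does not suggest skew.

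**3. Do the documents show zeros?** No. With three people, the lowest value is at most 65 − 80/√3 = 18.8 minutes. That is low, but it is not zero.

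**4. How often does the scale change significance?** These are 10,000 simulated trials per scenario with ANCOVA on baseline only. The additive effect is 0.61 × 97.3 = 59.4 min/week, and the half-responder case gives that gain on average. The proportional effect is ×2.05. That factor raises the treated SD to 2.05 × 97.3 = 199.5, so the pooled SD is √((97.3² + 199.5²)/2) = 156.9 and d = (1.05 × 91)/156.9 = 0.61.

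| Effect | Zeros | Shape | Power, minutes | Power, log(y+1) | Differ on p < 0.05 |
|---|---|---|---|---|---|
| Additive | 0% | gamma / lognormal | 89% / 89% | 100% / 100% | 11% / 12% |
| Proportional | 0% | gamma / lognormal | 93% / 94% | 81% / 99% | 15% / 6% |
| Half respond | 0% | gamma / lognormal | 82% / 82% | 81% / 91% | 15% / 13% |
| Additive | 10% | gamma / lognormal | 89% / 89% | 100% / 100% | 11% / 11% |
| Proportional | 10% | gamma / lognormal | 92% / 94% | 49% / 55% | 44% / 41% |
| Half respond | 10% | gamma / lognormal | 82% / 83% | 72% / 72% | 21% / 23% |
| Proportional | 20% | gamma / lognormal | 92% / 93% | 30% / 30% | 63% / 64% |

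Adding log(y+10) as a third analysis gives disagreement of about 6-16% with no zeros. With 10% zeros and a proportional effect it gives 43-45%.

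The proportional rows depend on how the effect is defined. A factor of 1.65 (59.4 minutes on a mean of 91) gives a treated SD of about 161 and a pooled d of about 0.45, below the plan's 0.61. No-zero disagreement is then about 27% (gamma) and 20% (lognormal).

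**5. Type I error.** With any one scale fixed it is 4.1-5.3%, and for minutes/week 4.1-5.0%. Choosing the more favourable of minutes and log(y+1) by result would give 6.9-8.4%, and up to 9.8% if the constant were free as well. These are upper bounds for choosing by result.

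**6. Which scale does the text imply?** Table 10 gives minutes/week as the unit, Hypothesis 1 is about a mean, and the pilot power scenario is in minutes/week. No passage states an effect, hypothesis or power on a log scale.

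**The case for a change.** The strongest argument for a change is that the cost is tiny and the choice is not neutral. Power moves in both directions: logs win for an additive effect or a lognormal shape without zeros, and minutes win for a proportional effect when some people record nothing. No reader could call the choice immaterial. The text expressly permits leaving the default, and it does not say the look is blind to arm. Two sentences would close this.

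Most of that is true as description. The plan is open on scale and silent on zeros, and a trial report would be clearer for saying which scale was used and why.

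The step from there to a defect is weaker. The largest figures rest on a zero share that the documents do not give, joined to an effect from which nobody at zero can benefit; the same zeros with an additive effect give 11%. Disagreement means only that one p value falls below 0.05 and another above it. In the additive and proportional runs checked for direction, no trial gave significant results in opposite directions. The plan also has the distribution examined before the aim analyses, so choosing by p value would depart from its stated order. Finally, either scale is acceptable once chosen, so the remedy would only record a choice the rest of the plan already implies.

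**Conclusion.** No change follows. The wording in 12.3j is a permissive clause that an analyst can fill sensibly from the rest of the plan: ANCOVA on minutes/week, with every participant kept. In all the simulated scenarios at the plan's effect size, including those with zeros, that analysis had 82-94% power and type I error of 4.1-5.0%. Skew therefore does not force a log, and on the minutes scale zero weeks need no special handling.

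The choice could matter to the extent of about 6-16% of trials with no zeros. With zeros and a proportional effect it would matter much more: 41-45% at 10% zeros and 63-64% at 20%. All of these rest on the assumed correlation of 0.5, the assumed shapes and an ANCOVA without the other covariates. The moments behind them come from only 12 people, 58% of them with T2D. The result shows sensitivity to an analyst's choice. It does not show that the planned test is invalid or that its stated power is wrong.

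The Table 10 wording is a clerical slip. Table 9, the pilot and the pilot power scenario all use combined moderate-to-vigorous minutes, and Table 10 has one primary row, so the intended variable is clear.

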12.3 APPROACH

12.3a. OVERALL RCT STUDY DESIGN The overarching goal of this proposed research is to determine whether an evidence-based intervention that is reimbursable in U.S. clinics will improve physical activity and physical function. To our knowledge, no studies have fully integrated these research programs into clinical practice. Thus, we designed this study to determine the effectiveness (Aim 1) and acceptability/time burden (Aim 2) of integrating an intervention for adults with T2D. For Aims 1-2, we will assess outcome measures at time = 0 (baseline) and time = 3 months (post-intervention). We provide a detailed timeline for our proposed research procedures (Table 5) to complement the timeline of training and career development activities in section 4. (Career Development Plan)

Table 5. K23 project timeline

	Year											
	Quarter				Year 2 – 2016				Year 3 – 2017			
Quarter	1	2	3	4	1	2	3	4	1	2	3	4
Project Phase												
Adaptation of screening and intervention for primary care	x	x										
Pilot-test intervention		x										
Patient recruitment and Screening		x	x	x	x	x	x	x	x	x	x	
Randomization of patients to intervention or usual care with accumulated participant goal (n) per quarter		5	20	35	50	65	80	100	115	130		
Data analyses of primary and secondary outcomes (Aim 1)											x	x
Process measure evaluation in participants and clinic system (Aim 2)			x	x	x	x	x	x	x	x	x	
K23 milestones: future grant submissions and manuscripts. See Table 3 timeline in “Career Development plan”		A			B		R01			R01		C

12.3b. ADAPTATION OF THE SCREENING ALGORITHM AND INTERVENTION FOR PRIMARY CARE

Because we are adapting the pilot CU LIFE intervention that is currently coordinated by research staff, we will need a pre-RCT adaptation phase to fully integrate the study procedures into the clinic. In this adaptation phase, the PI will meet monthly with an expert advisory team representing K23 mentors in physical activity in T2D ([name]), endocrinology ([name]), physical therapy ([name]), physical activity behavior counseling ([name]), health promotion clinic staff who will deliver the counseling, and clinic physician assistants who will conduct the screening and monitor the treatment.

Clinical screening algorithm (Table 6): First, we will optimize the clinical screening algorithm in consultation with our expert advisory team. Next, in months 4-6, the PI will train four clinic physician assistants (n = 2 from

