Physical function	The Short Physical Performance Battery (SPPB) measures function with the following valid subscales: balance, usual walking speed, and repeated chair rise. The SPPB is sensitive to change for adults with moderate to severe functional impairment , and predicts disability and mortality. ^{68,89}	Ordinal, range 0-12	Aim 1 2° outcome
Lower extremity strength	Lower extremity strength will be measured as leg extensor (quadriceps) and leg flexor (hamstring) strength using [name] laboratory's established techniques. ^{38,90}	Continuous	Aim 1 Function predictor
Grip strength	Hand grip strength will be measured by dynamometer. ⁹¹	Continuous	Aim 1 2° outcome
Metabolic control outcome			
Hemoglobin A1c	Average glycemic control measured by standard methods ⁹²	Continuous	Aim 1
Covariates for adjustment			
Depression symptoms	Center for Epidemiologic Studies Depression Scale measures depressive affect severity and is valid in people with ^{93,94} and without T2D. ^{95,96}	Continuous	Aim 1 covariate for adjustment
Lower extremity arthritis pain symptoms	Western Ontario and McMaster Universities Arthritis Index—valid measure of knee and hip pain and stiffness. ⁹⁷	Continuous	Aim 1 covariate
Cognitive processing speed	Stroop test –measures cognitive processing speed as a valid predictor of cognitive function in adults with and without T2D. ⁹⁸⁻¹⁰⁰	Continuous	Aim 1 covariate

DEXA scan	DEXA will allow the calculation of body composition as fat-free mass and total mass so that we may report exercise performance levels standardized to these body composition measures.	Continuous	VO ₂ max covariate for adjustment
Cognitive executive function	Behavioral Dyscontrol Scale – valid measure of executive function in adults with and without T2D. ^{101,102}	Continuous	Aim 1 covariate
Process outcomes			
Acceptability	Percent of intervention patients who would recommend intervention ¹⁰³ ; Percent of clinical providers/staff who recommend continuing to offer the intervention to patients ¹⁰³	Percentile	Aim 2
Time burden	Patient time required for each intervention visit ¹⁰³ ; Staff/provider time required for each intervention visit ¹⁰³	Continuous	Aim 2
Safety outcomes			
	Participant report of outcomes after baseline testing: falls, musculoskeletal injuries, foot ulcers, hypoglycemia ^{20,24,57}	Continuous	Safety

12.3k. ANALYSIS OF ACCEPTABILITY OUTCOMES (Aim 2 and Safety analysis)

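### The secondary effect sizes are defined on unadjusted 3-month means; basing them on the own-baseline-adjusted difference, over a named SD, would give more precision at no cost

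*Combined protocol and SAP*

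**What the plan says.** Section 12.3j, under Aim 1 secondary outcomes, defines the effect size as a Cohen's "d effect size comparing the means of the two groups at the three-month follow-up". No baseline adjustment is mentioned, and the SD that divides the difference is not named.

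The next sentence reads "We will use separate ANCOVA models to assess pre-post intervention changes in the following outcomes listed in Table 10". The outcomes it lists are the 400-meter walk, the SPPB, the Social Cognitive Theory constructs, lower extremity strength and HbA1c. It gives no covariates and does not say that d comes from these models. VO2max ("To assess cardiorespiratory fitness, we measure breath-by-breath utilization of oxygen") and grip strength ("Hand grip strength will be measured by dynamometer") are marked as Aim 1 secondary outcomes in Table 10 but are not in the list. Table 10 does mark DEXA as an adjustment covariate for VO2max, to "report exercise performance levels standardized to these body composition measures".

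For the primary outcome, the same section includes the baseline score in the ANCOVA and gives the reason: "Adjustment for baseline score is useful in this relatively small RCT to eliminate any potential baseline differences between groups". Section 12.3a and Table 8 schedule outcome testing at baseline and at 3 months in both arms.

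The secondary analyses "will be used to detect trends and to provide necessary data to calculate the sample size needed to detect differences in a larger RCT". The Aim 1b power text expects the sample to give an accurate effect size for physical function. Section 12.3m says the follow-on R01 will be powered on physical function if these data suggest a benefit.

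**The concern.** The plan recognises that arms of this size can differ at baseline by chance and corrects for it in the primary outcome. It then defines the secondary effect size from follow-up means alone, although the same participants have baseline values for those outcomes. The estimate is therefore noisier than it need be, and any chance baseline difference carries into it in proportion to the pre-post correlation.

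The definition also leaves room for choice. One analyst could report a d from 3-month means, another from the ANCOVA over a raw SD, and a third from the ANCOVA over the residual SD. The third number is systematically larger than the other two.

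Two later uses are at stake: the judgement whether function improved, and the sizing of the larger trial.

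**Working it through.** **Inputs from the documents.** 1:1 allocation; 90 evaluable (45 per arm); 130 enrolled (65 per arm); two-sided alpha 0.05; planning d = 0.61 for the primary outcome.

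**Assumed input.** The documents give no pre-post correlation r for any secondary outcome, so r = 0.3, 0.5, 0.7 and 0.8 are used. The r = -0.52 in section 12.3h relates activity to walk time, so it is not a pre-post correlation.

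**The plan's own figures reproduce.** At 45 per arm and d = 0.61, power is 82.5% (normal) or 81.6% (noncentral t), against a stated value of over 80%. Enrolment: 90/0.70 = 128.6, so 129 against a stated 130. No precision is stated for the secondary effect sizes.

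**1. Precision.** In SD units, for n per arm and d near zero:
- unadjusted half-width = t(0.975, 2n-2) × sqrt(2/n)
- adjusted half-width = t(0.975, 2n-3) × sqrt((2/n)(1-r²))
- total N giving the same precision unadjusted = 90/(1-r²)

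Unadjusted, 45 per arm gives 1.987 × sqrt(2/45) = 1.987 × 0.2108 = 0.419 (0.413 by the exact noncentral-t interval). At 65 per arm it is 0.347 (0.344 exact).

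| r | Adjusted, 45/arm | Narrower than 0.419 | Equivalent total N | Adjusted, 65/arm |
|---|---|---|---|---|
| 0.3 | 0.400 | 5% | 99 | 0.331 |
| 0.5 | 0.363 | 13% | 120 | 0.301 |
| 0.7 | 0.299 | 29% | 176 | 0.248 |
| 0.8 | 0.251 | 40% | 250 | 0.208 |

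**2. Chance imbalance.** The baseline difference between arms has SD sqrt(2/45) = 0.211. The chance that it exceeds 0.20 SD in either direction on any one outcome is 2 × [1 - Φ(0.20/0.211)] = 0.34. An imbalance of 0.20 SD shifts the unadjusted d by r × 0.20 = 0.06, 0.10, 0.14 or 0.16. The adjusted estimate is not shifted.

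**3. Simulation** (6,000 trials per r, 45 per arm, bivariate normal, true d = 0.30).
- The unadjusted d and the adjusted difference over an unadjusted SD both average 0.30 to 0.31, so they target the same quantity.
- The SD of the estimate is 0.21 to 0.22 unadjusted, against about 0.21, 0.19, 0.15 and 0.13 adjusted.
- At r = 0.7, in trials with baseline imbalance above +0.20 SD or below -0.20 SD, the unadjusted d averages 0.53 or 0.09. The adjusted estimate averages 0.31 or 0.30.

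**4. Divisor.** Dividing the adjusted difference by the ANCOVA residual SD gives approximately d/sqrt(1-r²). For a true 0.30 the simulated averages are 0.32, 0.35, 0.43 and 0.50.

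This matters for sizing the next trial. At d = 0.30, two-sided 0.05 and 80% power, it needs 176 per arm unadjusted. If it uses ANCOVA (assumed), it needs 176 × (1-r²) = 132, 90 or 64 per arm at r = 0.5, 0.7 or 0.8. At r = 0.8, a residual-SD d of 0.50 already leads to 64 per arm. If it were mistaken for an ordinary d and discounted again, the answer would be 64 × 0.36 = 23 per arm.

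**5. SPPB.** This is an ordinal 0-12 score. Assume a latent SD of 2 points, rounding, and a cap at 12 that puts 31% or 50% of participants at the maximum. At latent r = 0.7 the adjusted half-width is then 0.32 to 0.33 rather than 0.30.

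**The case against.** - **ANCOVA is already planned.** The plan has ANCOVAs of pre-post change for most function outcomes, directly after a paragraph that adjusts the primary outcome for baseline. Carrying that specification forward is natural, and comparing group means does not exclude adjusted means. This stands in part: an adjusted difference may be produced for the listed outcomes. But the effect size has its own sentence, based on 3-month means, and VO2max and grip strength have no listed model.
- **There is no error.** The unadjusted d is unbiased and these are trend-seeking secondary analyses. True; this is a gain in efficiency and clarity, not a correction of bias.
- **The size rests on an undocumented r.** This stands. The gain runs from negligible to 40%, and nothing in the documents places any outcome in that range.
- **The next trial stays uncertain.** This also stands. An observed d of 0.30 has an interval of -0.12 to 0.72 unadjusted, and still about 0.00 to 0.60 adjusted at r = 0.7. The improvement is real but does not make the estimate precise.
- **Baseline testing may follow randomisation.** Section 12.3e puts randomisation after consent at the enrolment visit, Table 8 puts baseline testing mainly at visits 2-3, and the flow figure is not shown. If participants know their allocation when tested, effort-dependent baseline values could be affected. The results above assume that they are not.

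**Conclusion.** The concern holds. As written, the secondary effect size ignores baseline values that are collected in both arms, and its divisor is undefined. The reason the plan gives for adjusting the primary outcome applies equally to these outcomes.

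At 45 per arm the 95% half-width would fall from about 0.42 SD to between 0.40 and 0.25 SD for r from 0.3 to 0.8. The gain is worth having from about r = 0.5. The results rest on the assumed r, approximate normality (only rough for the SPPB) and baseline values unaffected by allocation.

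The trial remains valid without the change, and the primary test, its power and the safety analysis are unaffected. The change should be made because it is free and because these estimates are meant to inform the next trial.

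**What to change.** In section 12.3j, Aim 1 secondary outcomes:

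1. Define the effect size as the ANCOVA group difference at 3 months, adjusted for that outcome's own baseline value, divided by an unadjusted SD, with its 95% CI. Name one SD in advance, either pooled baseline or pooled follow-up, and not the ANCOVA residual SD. What is fixed is the choice of SD, not its numerical value.
2. State the own-baseline covariate for every secondary ANCOVA, and add VO2max and grip strength to the list.
3. Report the pre-post correlation or residual SD for each outcome, so that the next trial can be sized for an adjusted or an unadjusted analysis.
4. Describe the SPPB effect size as approximate because the score is ordinal.

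As a minor accompanying edit, replace the claim of accuracy in the Aim 1b power text with the expected precision: about ±0.41 SD (exact) or ±0.42 SD (t-based), unadjusted, at n = 90.

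The cost is a few sentences and two further models on data already scheduled for collection, with no extra participants, visits or measurements.
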